3. OBJECTIVES AND ENDPOINTS

Table 2 Study objectives and endpoints

Primary Objective:	Endpoint/Variable:
To evaluate the efficacy of inhaled AZD8871 600 µg in patients with moderate to severe COPD	
Primary
 
 • Change from baseline in Trough FEV₁ on Day 15. 
Secondary
 
 • FEV₁ AUC_{(0-4)/4h} (area under the curve for the change in FEV₁ from baseline to 4h, normalised by the time window) at Day 1, Day 8, and Day 14. • FEV₁ AUC_{(0-8)/8h}, AUC_{(0-12)/12h}, and AUC_{(0-24)/24h} at Day 1 and Day 14. • Change from baseline in Trough FEV₁ on Day 2, and Day 8. • Change from baseline in Peak FEV₁ on Day 1, Day 8 and Day 14. • Change from baseline in Trough FEV₁ over treatment duration. • Change from baseline in Peak FEV₁ over treatment duration. • Change from baseline in Total Score of BCSS questionnaire and cough, breathlessness and sputum individual domain scores from Day 1 to Day 8, from Day 9 to Day 14 and during the whole treatment duration. • Change from baseline in CAT from Day 1 to Day 8, from Day 9 to Day 14 and during the whole treatment duration. • Rescue medication use from Day 1 to Day 8 and from Day 9 to Day 14.
Secondary Objective:	Endpoint/Variable:
To investigate the PK of AZD8871 600 µg and its primary metabolite after multiple dose administration of AZD8871 in patients with moderate to severe COPD	
On serial PK sampling days, the following PK parameters will be calculated for AZD8871 and its primary metabolite LAS191861 when applicable:
 
 • Day 1: Maximum plasma concentration (C_{max}), time to reach maximum plasma concentration (t_{max}), area under the plasma concentration-curve from time 0 to the time of last quantifiable concentration (AUC_{last}), area under the plasma concentration-curve from time 0 to 24 hours post-dose AUC₍₀₋₂₄₎. • Day 14: C_{max}, t_{max}, AUC_{last}, AUC₍₀₋₂₄₎, average plasma concentration during a dosing interval (C_{avg}), fluctuation index during a dosing interval (%Fluctuation), accumulation ratio for C_{max} [Rac(C_{max})] and accumulation ratio for AUC₍₀₋₂₄₎ [Rac(AUC₍₀₋₂₄₎)]. 
Additional parameters may be determined where appropriate.

Safety Objective:	Endpoint/Variable:

To evaluate the safety and tolerability of inhaled AZD8871 600 µg in patients with moderate to severe COPD	
 • AEs/SAEs. • Vital signs. • ECG. • Clinical laboratory assessments.
Exploratory objective:	Endpoint/variable:
To evaluate patient's response to inhaled AZD8871 600 µg in patients with moderate to severe COPD	
 • COPD exacerbations. • Cough VAS. • Cough monitoring. • CCI

4. STUDY DESIGN

4.1 Overall design

This is a randomised, placebo-controlled, double-blind, 3-way complete crossover William's design, international, multi-centre Phase IIa multiple dose study of 1 dose level of AZD8871, an active comparator (Anoro[®] Ellipta[®]) and placebo administered by DPI devices. Approximately 72 eligible male and non-childbearing female patients with moderate to severe COPD before randomisation and fulfilling all of the eligibility criteria will be randomised in a 1:1:1:1:1:1 to 1 of 6 treatment sequences. The study includes 12 visits and the entire study period is scheduled to take from a minimum of 6.5 months (182 days) to a maximum of 7.5 months (217 days) for each individual patient. The aim is to ensure at least 54 patients complete the study.

A subset of 36 patients, who will have specifically consented for pharmacokinetics (PK), will undergo PK assessments.

The study will be conducted at approximately 5 sites in Germany and the UK. Estimated study duration is 12 months.

The study will consist of a Screening period, 3 treatment periods (each separated by a wash-out period), and a Follow-up Visit, as described below.

Screening period: This will last up to 28 days and consists of 2 Screening visits (Visit 1 and Visit 2) and a run-in period.

Patients will be requested to stop their usual COPD therapy after signing the ICF at Visit 1 and will be maintained on a mono-component ICS therapy, if required. Patients that were taking any LAMA will be maintained with ipratropium (20 µg × 2 puffs 4 times per day) between Visit 1 and Visit 2. In addition, salbutamol 100 µg will be provided as rescue medication during the study as needed (rescue medication has to be discontinued 6 hours before any pulmonary function test). Visit 1 and Visit 2 could be performed on the same day if no wash-out of prior medication is required and the patient visits the site in fasting

condition. In case any wash-out of prior medication is required, then Visit 2 will be performed after the wash-out is complete.

All the screening assessments can be performed at Visit 1 or Visit 2, based on the site's preference, except for the following:

- ICF: This must be completed at Visit 1 before any study-specific assessments are performed.
- Reversibility test with salbutamol and spirometry (to confirm inclusion criterion #6); this must be performed at Visit 2 due to wash-out requirements.

If the FEV₁ predicted value is fulfilled according to inclusion criteria, the patient will be started on run-in period to assess clinical stability. If the FEV₁ predicted value is not met, pulmonary function tests could be rescheduled at the latest, up to Day -14.

The duration of run-in period will be between a minimum of 14 and a maximum of 28 days (from Visit 2 to Visit 3). During the run-in period, all patients will receive ipratropium 20 µg × 2 puffs 4 times per day (must be discontinued 8 hours prior to previous any pulmonary function test). A paper diary will be used to collect AEs and concomitant medication during run-in and wash-out periods.

Treatment periods: After the screening period, patients must fulfil all inclusion criteria and no exclusion criteria prior to being randomised at Visit 3. Eligibility results will be used from the Screening period for any assessments that cannot be completed within Visit 3 (eg, laboratory assessments).

The duration of each treatment period will be 14 days. In each treatment period, patients will receive 1 of the following 3 treatments according to a William's design with 3 periods and 6 sequences, using a balanced randomisation ratio per treatment sequence:

- AZD8871 600 µg once daily (double-blind).
- Anoro[®] Ellipta[®] (55 µg UMEC/ 22 µg VI) once daily (double-blind).
- Placebo (double-blind).

Each of the 3 treatment periods will include 2 overnight stays at the study site and 1 ambulatory visit at the study site.

Visits 3, 6 and 9 (corresponding to Treatment Day 1 in each period) and Visits 5, 8 and 11 (corresponding to Treatment Day 14 in each period) will include an overnight stay in the unit. At these visits, safety and tolerability assessments and pulmonary function measurements will be taken pre-dose and up to 24 hours post-dose.

Visits 4, 7 and 10 (corresponding to Treatment Day 8 in each period) will have duration of approximately 5 hours where safety and tolerability assessments as well as spirometry measurements will be performed pre-dose and up to 4 hours post-dose.

Study treatment administration during all the visits at the sites (Day 1, Day 2, Day 8, and Day 14 of each treatment period) will be supervised by study personnel.

At Visits 3 to 11, a subset of 36 patients will undergo PK assessments. Blood samples will be collected pre-dose and up to 24 hours post-dose.

On Day 1 of treatment periods 2 and 3, a FEV₁ stability test will be performed pre-dose. FEV₁ stability check will be based on the pre-BTR. At Visits 6 and 9 the mean of the pre-dose FEV₁ (mean of the 2 measured values) should be within (\pm)20% or (\pm)200 mL compared to the pre-dose FEV₁ (mean of the 2 measured values) of the first treatment period (Visit 3).

Study treatment administration compliance will be recorded in the e-Diary of the patient when the patient is not at the site. No dose modification is planned for this study.

Wash-out periods: Between each treatment period, there will be a wash-out period of 42 to 49 days. During this period, all patients will receive ipratropium 20 μ g \times 2 puffs 4 times per day (must be discontinued 8 hours before any pulmonary function test).

A paper diary will be used to collect AEs and concomitant medication during run-in and wash-out periods.

Follow-up Visit: Patients will come to the site for a Follow-up Visit, 42 days (up to 49 days) after the last IP administration, for AE assessment, safety laboratory, ECG, vital signs and physical examination.

For an overview of the study design see [Figure 1](#), Section 1.3. For details on treatments given during the study, see Section 6.1 Treatments Administered.

For details on what is included in the efficacy and safety endpoints, see Section 3 Objectives and Endpoints.

4.2 Scientific rationale for study design

The objective of the study is to assess the efficacy, safety and pharmacokinetics (PK) of AZD8871 600 μ g after a 14-day treatment period in patients with moderate to severe COPD. The target population includes male and female (non-childbearing potential) adult patients with clinical diagnosis of moderate to severe COPD as per the criteria of the GOLD guidelines.

A double-blinded, double-dummy design has been chosen to limit the occurrence of conscious and unconscious bias in the conduct and interpretation of a clinical study arising from the influence which the knowledge of treatment may have on the recruitment and allocation of patients. It is considered the optimal approach according to International Conference on Harmonisation (ICH) E9 “Statistical principles in clinical studies.”

The crossover design has been chosen to avoid inter-patient variability and optimize sample size. Based on the information of terminal elimination half-lives observed for AZD8871 and LAS191861 from previous clinical studies, the wash-out period proposed for this current study is a minimum of 42 days and up to 49 days in order to avoid any carry-over effect between periods.

By randomly assigning treatment sequence, differences in baseline characteristics of the treatment groups will be minimised. The inclusion of a placebo arm is considered the most reliable method to minimise patient and Investigator bias according to ICH Topic E10 (Choice of control group in clinical trials) ICH/364/96 guideline adopted by the Committee for Proprietary Medicinal Products (CPMP), CPMP/EWP/562/98 and Food and Drug Administration (FDA).

AZD8871 will be evaluated by directly comparing it against Anoro[®] Ellipta[®]; the best-in-class once daily LAMA and LABA fixed-dose combination ([Feldman et al, 2017](#)).

Since COPD patients present with multiple comorbidities, a placebo arm has been added to better characterise the safety profile of the product. The inclusion of a placebo treatment will enhance the interpretation of the difference in safety and efficacy outcomes between active arms. This is due to the limited available data for Anoro[®] Ellipta[®] in this specific COPD patient population and the endpoints that will be assessed.

4.3 Justification for dose

The proposed dose level of AZD8871 in this study is 600 µg of AZD8871 given by inhalation once daily during 14 days through a multi-dose DPI device. The dose has been selected based on the safety, tolerability, efficacy, and PK information generated in previous clinical studies. The study drug released in this study will differ to previous trials due to the addition of Magnesium Stearate – required in multi-dose device setting - and slight changes in production processes. It is estimated these changes will have limited impact to the clinical outcome.

4.4 End of study definition

The end of study is defined as the last expected visit/contact of the last patient undergoing the study.

A patient is considered to have completed the study when he/she has completed his/her last scheduled visit.

See Appendix [A 6](#) for guidelines for the dissemination of study results.

5. STUDY POPULATION

Patients will be recruited from early phase clinical unit sites via internal databases and local advertisement. Investigator(s) should keep a record, the patient screening log, of patients who entered pre-study screening.

Prospective approval of protocol deviations to recruitment and enrolment criteria, also known as protocol waivers or exemptions, is not permitted.

Each patient should meet all of the inclusion criteria and none of the exclusion criteria for this study in order to be assigned/randomised to a study treatment. Under no circumstances can there be exceptions to this rule. Patients who do not meet the entry requirements are screen failures, refer to Section 5.4.

In this protocol, “enrolled” patients are defined as those who sign informed consent. “Randomised” patients are defined as those who undergo randomisation and receive a randomisation number.

For procedures for withdrawal of incorrectly enrolled patients see Section 7.3.

5.1 Inclusion criteria

Patients are eligible to be included in the study only if all of the following inclusion criteria and none of the exclusion criteria apply:

Informed consent

1. Provision of signed and dated, written ICF prior to any study-specific procedures, sampling, and analyses.

The ICF process is described in Appendix A 3.

Age

2. Patient must be 40 to 85 years of age (both inclusive) at the time of signing the ICF (Screening; Visit 1).

Type of patient and disease characteristics

3. COPD Diagnosis: Patient with an established clinical history of moderate to severe COPD for more than 1 year at Screening, according to the GOLD COPD guidelines.
4. Tobacco Use: Patient is a current or former smoker with a history of ≥ 10 pack-years of cigarette smoking [Number of pack-years=(number of cigarettes per day/20)* number of years smoked (eg, 1 pack-year=20 cigarettes smoked per day for 1 year)]. A former smoker is defined as one who has stopped smoking for at least 6 months prior to Screening.
 - Patient smoking other tobacco types (including e-cigarettes) will not be allowed, unless he/she meets the cigarette criterion as well.
5. Patient with post-bronchodilator FEV₁/forced vital capacity (FVC) ratio <70% based on the value reached after inhalation of salbutamol (400 µg) at Visit 2. If criterion is not met, the test can be repeated at the latest, up to Day -14.

6. Patient with post-bronchodilator FEV₁ that must be $\geq 40\%$ and $< 80\%$ predicted normal value at Visit 2. If the criterion is not met, the test can be repeated at the latest, up to Day -14.
7. Patient is willing and, in the opinion of the Investigator, able to change current COPD therapy as required by the protocol and willing to use ipratropium following the approved dosage and regimen (during run-in and wash-out periods) with or without ICS for maintenance therapy of COPD and rescue medication salbutamol (as needed) from Visit 1 to Visit 11.
8. Patient must be able to read, speak and understand local language, and be willing to remain at the study centre as required per-protocol to complete all visit assessments.

Weight

9. Body mass index (BMI) $< 40 \text{ kg/m}^2$ at the time of Screening.

Sex

10. Male and/or females of non-childbearing potential who are not pregnant or lactating.

Reproduction

11. Female patients must be of non-childbearing potential defined as:
 - Permanently or surgically sterilised, including hysterectomy and/or bilateral oophorectomy and/or bilateral salpingectomy.
 - Post-menopausal; aged < 50 years and amenorrhoeic for 12 months or more following cessation of exogenous hormonal treatments and with luteinizing hormone (LH) and follicle stimulating hormone (FSH) levels in the post-menopausal range of the local laboratory.
 - Post-menopausal; aged ≥ 50 years and amenorrhoeic for 12 months or more, following cessation of all exogenous hormonal treatments.
12. Male patients should use a condom and spermicide (or sexual abstinence*) to prevent pregnancy and drug exposure of a partner, regardless of the gender or childbearing potential of the partner from the day of the first administration of the IP until 3 months after the last administration of the IP. In addition to a condom with spermicide, a second highly effective method of contraception (oral, intravaginal or transdermal hormonal contraceptives, intrauterine device, or intrauterine hormone-releasing system until 3 months after the last administration of the IP) should be used with female partners of childbearing potential. Double barrier methods (a combination of male condom with either a cap, diaphragm or sponge with spermicide) are not considered to be highly effective methods of contraception. Male patients with a pregnant partner should use a condom and spermicide or sexual abstinence*.

*True abstinence: When this is in line with the preferred and usual lifestyle of the subject. (periodic abstinence [eg, calendar, ovulation, symptothermal, post-ovulation methods], declaration of abstinence for the duration of a trial, and withdrawal are not acceptable methods of contraception).

 - Unstable angina or unstable arrhythmia which has required changes in the pharmacological therapy or other intervention within 12 months prior to Screening (Visit 1), or newly diagnosed arrhythmia within the previous 3 months prior to Screening (Visit 1).
 - Second degree atrio-ventricular block.
 - Use of pacemaker.
 - Hospitalisation within 12 months prior to Screening (Visit 1) for heart failure functional classes III (marked limitation of activity and only comfortable at rest) and IV per the “New York Heart Association”.
11. Patient with a QT interval corrected using Fridericia's formula (QTcF) value >450 ms for male and >470 ms for female or an ECG that is not suitable for QT measurements (eg, poorly defined termination of the T wave).
12. Patient with a heart rate <50 or >100 beats per minute (bpm).
13. Patient has clinically significant uncontrolled hypertension (>160 mmHg) as assessed by the Investigator.

Neurological:

14. Patient has seizures or a history of seizures requiring anticonvulsants within 12 months prior to Screening.
15. Patient is taking selective serotonin reuptake inhibitors or serotonin-norepinephrine reuptake inhibitors whose dose has not been stable for at least 4 weeks prior to Screening, or exceeds the maximum recommended dose.

Renal/Urogenital:

16. Patient has a symptomatic bladder neck obstruction, acute urinary retention or symptomatic non-stable prostate hypertrophy.

Other:

17. Any laboratory abnormality or suspicion of any clinically relevant disease or disorder (on history or examination), including uncontrolled diabetes or hypokalaemia (serum potassium <3.5 mmol/L), which, in the opinion of the Investigator, may either put the patient at risk because of participation in the study, or influence the results or the patient's ability to participate in the study (eg, severe hepatic impairment) or any other safety concerns in the opinion of the Investigator. Note: Potassium replacement and re-test is allowed once if serum potassium concentration was <3.5 mmol/L at Screening or prior to randomisation.
18. Patient has known human immunodeficiency virus (HIV) infection or chronic hepatitis B or C infection.
19. History of malignancy of any organ system, treated or untreated within the past 5 years, with the exception of localised basal cell carcinoma of the skin.
20. Patient has known narrow-angle glaucoma.
21. Patient has a history of drug of abuse within the past 2 years or consuming more than 14 (female patients) or 21 (male patients) units of alcohol a week, or shows positive for drugs of abuse and alcohol tests at Screening and prior to randomisation.

Note: If a patient tests positive to any drugs of abuse tests, which cannot be explained by use of prescription medication, he/she will be excluded from the study. Unit=1 glass of wine (125 mL)=1 measure of spirits=½ pint of beer.

22. Patient has a history of hypersensitivity (including paradoxical bronchospasm) to β_2 -agonists, muscarinic anticholinergics or lactose/milk protein. Lactose intolerance is not an exclusion criterion.

Prior/concomitant therapy

23. Patient has received a live attenuated vaccination within 30 days prior to Screening.

Note: Inactivated influenza vaccination, pneumococcal vaccination, or any other inactivated vaccine is acceptable provided it is not administered within 7 days prior to Screening or randomisation (Visit 3).

24. Patient who, in the opinion of the Investigator, is unable to abstain from protocol-defined prohibited medications during the study.

Prior/concurrent clinical study experience

25. Patient was treated with an investigational drug or device in another clinical trial within the last 30 days or 5 half-lives (whichever is longer) prior to Screening.

Note: Patient participation in observational studies (ie, studies that do not require change to medication or an additional intervention) is not exclusionary.

26. Previous participation or prior screen failure in the present study.

Other exclusions

27. Involvement in the planning and/or conduct of the study (applies to both AstraZeneca staff and/or staff at the study site).
28. Patient has changed their smoking status (ie, restarted or stopped smoking) or initiation of a smoking cessation program within 6 weeks of Screening.
29. Patient has participated in the acute phase of a pulmonary rehabilitation program within 4 weeks prior to Screening or who will enter the acute phase of a pulmonary rehabilitation program during the study. A patient in the maintenance phase of a pulmonary rehabilitation program is not to be excluded.
30. Judgment by the Investigator that the patient should not participate in the study if the patient is unlikely to comply with study procedures, restrictions and requirements. Inability to comply with requirements includes having an e-Diary completion rate of <70% during the run-in period.
31. Patient who have donated or lost >500 mL of blood and/or plasma within the previous 3 months prior to Screening.
32. Vulnerable patients (who has been placed in an institution due to a regulatory or court order).

Procedures for withdrawal of incorrectly enrolled patients see Section 7.3.

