5.4 Screen failures

Screening failures are defined as patients who signed the ICF to participate in the clinical study but are not subsequently randomly assigned to study treatment. A minimal set of screen failure information is required to ensure transparent reporting of screen failure patients to meet the Consolidated Standards of Reporting Trials (CONSORT) publishing requirements and to respond to queries from regulatory authorities. Minimal information includes demography, screen failure details, eligibility criteria, and any SAE.

Individuals may be rescreened only if the patient has not failed any assessment but was not randomised within the screening window (28 days of their first assessment). Individuals who do not meet the eligibility criteria (despite the repeated tests) will be screen failed. Repetition of the entire Screening Visit is not allowed. Rescreened patients should be assigned the same patient number as for the initial screening. However, rescreening should be documented so that its effect on study results, if any, can be assessed.

These patients should have the reason for study withdrawal recorded in the electronic Case Report Form (eCRF).

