27	Patient with symptomatic bladder neck obstruction, acute urinary retention or symptomatic non-stable prostate hypertrophy.	Yes	No	No	No
28	Patient has a serum potassium value <3.5 mmol/L at Screening and on repeat testing, uncontrolled diabetes and any clinically relevant lab abnormality. Note: however potassium replacement and rescreening is allowed once if serum potassium concentration was <3.5 mmol/L at Screening.	Yes	No	No	No
29	History of malignancy of any organ system, treated or untreated within the past 5 years, with the exception of localised basal cell carcinoma of the skin.	Yes	No	No	No
30	Patient has known narrow-angle glaucoma.	Yes	No	No	No
31	Patient has a history of hypersensitivity to β_2 -agonists, muscarinic anticholinergics or lactose/milk protein. Lactose intolerance is not an exclusion criterion.	Yes	No	No	No
32	The patient has a history of drug of abuse within the past 2 years or consuming more than 14 (female patients) or 21 (male patients) units of alcohol a week, or shows positive for drugs of abuse and alcohol tests at Screening and/or prior to randomisation.	Yes	No	No	No
33	Patient received a live attenuated vaccination within 30 days prior to Screening.	Yes	No	No	No
34	Patient donated or lost >500 mL of blood and plasma within the previous 3 months prior to Screening	Yes	No	No	No
35	Vulnerable patients (who has been placed in an institution due to a regulatory or court order)	Yes	No	No	No
36	Patient is unlikely to co-operate with the requirements of the study, instructions of the Principal Investigator (PI), or have e-dairy completion rate of <70% during the run-in period.	Yes	No	No	No
37	Involvement in the planning and/or conduct of the study (applies to both AstraZeneca staff and/or staff at the study site).	Yes	No	No	No
38	Patient previously enrolled in the present study	Yes	Yes	Yes	Yes
39	Patient has participate in the acute phase of a pulmonary rehabilitation program within 4 weeks prior to Screening or who will enter the acute phase of a pulmonary rehabilitation program during the study.	Yes	No	Yes	Yes
40	Patient non-compliance with study procedures, unable to change current COPD therapy as required by the protocol and not willing to use ipratropium following the approved dosage and regimen – as judged by the investigator.	Yes	No	Yes	Yes
41	Patient is unwilling to remain at the study centre as required per protocol to complete all visit assessments.	Yes ⁺⁺⁺	No	Yes ⁺⁺⁺	No

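### Protocol 5.4 permits rescreening of patients whom exclusion 26 bars, and SAP Table 1 item 38, read literally, drops such patients from every analysis set once they are randomised and dosed

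*Protocol*

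**What the plan says.** **Eligibility.** Protocol 5.2, exclusion 26, bars "Previous participation or prior screen failure in the present study". It makes no exception and does not refer to 5.4. Section 5 states that eligibility rules admit no exceptions or waivers.

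**Rescreening.** Protocol 5.4 states: "Individuals may be rescreened only if the patient has not failed any assessment but was not randomised within the screening window". The window is 28 days from the first assessment. Appendix A 3 repeats the permission and requires the patient to sign the consent form again. Section 5.4 adds that "Rescreened patients should be assigned the same patient number as for the initial screening" and that "rescreening should be documented so that its effect on study results, if any, can be assessed".

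**Definitions.** Protocol 5.4: "Screening failures are defined as patients who signed the ICF to participate in the clinical study but are not subsequently randomly assigned to study treatment". Protocol section 5: enrolled "patients are defined as those who sign informed consent".

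**Analysis sets.** SAP 2.2, Table 1, item 38 reads "Patient previously enrolled in the present study" and is marked Yes for exclusion from P-PS, SS, PKS and FAS. Item 50, for a screening failure who was given study drug, is marked the same way. SAP 2.1.1 puts every randomised patient who received IP in the FAS, whatever their adherence. SAP 2.1.2 puts every randomised patient with at least one dose in the safety set.

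**The concern.** Section 5.4 offers rescreening to one narrow group, and exclusion 26 appears to bar exactly that group. A site cannot follow both. If it follows 5.4, the patient may later be judged ineligible, and section 7.3 says that a treated patient found ineligible must stop treatment and be excluded from the study. If it follows exclusion 26, the permission in 5.4 and A 3 has no effect. Two sites could treat identical patients differently.

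The second stage matters more for the analysis. A patient rescreened, randomised and dosed as 5.4 allows could be dropped from the efficacy and safety sets through one table row. That would take a treated patient out of the intention-to-treat analysis and that patient's adverse events out of the safety tables, against the SAP's own definitions of those sets.

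**Working it through.** **Step 1: eligibility.** Take a patient who consented, failed nothing, and was not randomised within 28 days.

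- Under the 5.4 definition, being a screening failure needs only consent and no randomisation. It does not need a failed assessment. When the window lapses, this patient meets it.
- 5.4 and A 3 permit rescreening of this patient.
- Exclusion 26 bars any prior screen failure, and section 5 forbids exceptions.

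The conflict is complete for this group. It does not extend to patients who failed an assessment, because 5.4 does not let them be rescreened.

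**Step 2: item 38.** Enrolled means consent signed. The rescreened patient signed before and signs again. Read literally, the patient was previously enrolled and item 38 applies. The Table 1 footnote limits an exclusion to a time point or period, or leaves it to the data review, only for entries marked ++ or +++. Item 38 carries neither mark, so the exclusion covers the whole patient.

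**Step 3: comparison with the rest of Table 1.** Items 1 to 37 include true eligibility failures (age, FEV₁, FEV₁/FVC, QTcF), and all are No for SS and FAS. Item 53 concerns patients who took no IP. Items 38 and 50 are the only rows that take dosed patients out of the safety set. A patient who failed the FEV₁ criterion therefore stays in FAS and SS, while a patient rescreened as 5.4 allows would leave both.

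**Step 4: power, as an illustration.** Inputs from Protocol 9.2: difference 100 mL, SD of differences 220 mL, two-sided 5%, 54 evaluable, 25% dropout. For a paired t-test, power is P(|T| > t₀.₉₇₅,ₙ₋₁), where T is noncentral t with n − 1 degrees of freedom and noncentrality (100/220)√n.

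The plan's own figures reproduce: n = 54 gives noncentrality 3.340 and power 0.906, against the stated 90%; 54/(1 − 0.25) = 72.

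The number of rescreens is not given. Assume 3 or 6 completers are lost. At 25% dropout that corresponds to 3/0.75 = 4 or 6/0.75 = 8 randomised rescreens.

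| Completers lost (assumed) | n | Noncentrality | Power |
|---|---|---|---|
| 0 | 54 | 3.340 | 0.906 |
| 3 | 51 | 3.246 | 0.889 |
| 6 | 48 | 3.149 | 0.870 |

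**The case against.** The best defence reads the passages together. A window-lapse patient who is rescreened and randomised has, in the end, been randomly assigned, so need not count as a screening failure. Section 5 also uses the term more narrowly, for patients who do not meet the entry requirements. On that sense exclusion 26 bars eligibility failures and 5.4 covers lapsed windows. Because the patient number is kept, rescreening can be seen as one continuing enrolment, and item 38 as a rule against entering the same person twice. Table 1 lists deviations, and a rescreen that the protocol allows is not one. Finally, patients are lost only if a site applies 5.4 at entry and the analysis team then reads item 38 literally.

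Much of this stands as a plausible statement of intent. It means a reader should not infer that the plan certainly deletes every rescreened patient. Item 38 reaches them only through the definition of enrolled, and the blind data review might decide otherwise.

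It does not remove the problem. At the moment of rescreening the patient has consented and has not been randomised, which is the 5.4 definition. No passage says that rescreening continues one enrolment, and the second consent signature points the other way. The wish in 5.4 to assess the effect of rescreening on results presupposes that these patients are analysed. Even as a duplicate-entry rule, item 38 takes randomised, dosed persons out of FAS and SS, against SAP 2.1.1 and 2.1.2.

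**Conclusion.** The conflict between exclusion 26 and the rescreening permission in 5.4 and A 3 is in the text and must be reconciled. The loss from the analysis sets follows from a literal reading of item 38, and possibly item 50. It is a risk that the wording creates and nothing in the documents excludes; it is not a certain outcome.

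The size cannot be stated, because no rescreening count is given. On the assumed loss of 3 to 6 of 54 completers, power falls by 1.7 to 3.6 percentage points (90.6% to 88.9% or 87.0%). A reader might infer a serious threat to power, but these figures do not support that unless many patients are rescreened. Nor does each case necessarily cost a full three-period patient, since some would drop out or be stopped under 7.3. The main harm is that treated patients and their adverse events could leave FAS and SS, together with inconsistent eligibility decisions between sites.

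**What to change.** 1. **Protocol 5.2, no. 26.** Reconcile it with 5.4 and A 3, for example by excepting rescreens that 5.4 permits.
2. **SAP Table 1, item 38.** Limit it to persons previously randomised or treated in this study, and state that a rescreen under 5.4 is not a deviation.
3. **SAP Table 1, items 38 and 50.** Set SS and FAS to No, so that every randomised, dosed patient is kept. This does not bring in people who were never randomised, because SAP 2.1.1 and 2.1.2 already require randomisation.
4. **Duplicate rule.** Count a person randomised twice once in the FAS, under the first randomisation, and retain all their safety data. Without this rule, setting FAS to No could let one person enter the mixed model as two independent patients.

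The cost is one clarifying sentence in the protocol, changes to two SAP table rows and a short SAP rule, all to be settled before unblinding. No new data or added patients are needed.
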